9.2.2 Continuous Endpoints

For continuous efficacy endpoints where Mixed-Effect Model Repeat Measurement (MMRM) analysis or Analysis of Covariance (ANCOVA) is performed, missing data will be handled using the following approaches.

- MMRM: The repeat measurement analysis will be conducted using a mixed model including observed measurements at all post-baseline visits for the respective analysis period up to the end of the analysis period. The mixed model includes the categorical fixed effects of treatment, visit and treatment-by-visit interaction, stratification factors at randomization, and the continuous fixed covariates of baseline measurement. An unstructured variance covariance matrix will be used. If the model cannot converge, an appropriate variance-covariance structure matrix (e.g., autoregressive or compound symmetry) will be used. Parameter estimation is based on the method of restrictive maximum likelihood (REML). MMRM will be the primary approach in the analysis of continuous variables with repeated measurements.
- ANCOVA: For continuous efficacy variables that are collected at only one post-baseline visit (such as SES-CD), ANCOVA will be used. The model includes the categorical fixed effects of treatment, stratification factors at randomization, and the continuous fixed covariates of baseline and measurement.

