7.4 Statistical Analyses for Efficacy

Efficacy analysis will be performed by the subject's randomized treatment group. All statistical tests will be performed at a 2-sided significance level of 0.1. A 95% confidence interval (CI) of the treatment difference between each ABBV-154 dose and placebo will be provided. The actual value of stratification factors will be used in the analysis.

For categorical variables, pairwise comparison will be made between each ABBV-154 dose and placebo using the Cochran-Mantel-Haenszel (CMH) test, adjusting for stratification factors (Section 5.8). Non-responder imputation incorporating multiple imputation (NRI-MI) to handle COVID-19 will be the primary approach to handle missing data for categorical endpoints.

For continuous variables, the comparison will be made between each ABBV-154 dose and placebo based on the mixed effect model repeated measures (MMRM) adjusting for visit, interaction between

treatment and visit, actual values of stratification factors as fixed factors, and baseline value (of the Induction Period) as a covariate. The MMRM will be the primary approach to handle missing values for continuous endpoints.

Summary and Analysis of the Primary Endpoint

The primary endpoint is the achievement of endoscopic response at Week 12 of the Induction Period. Comparison of the primary endpoint will be made between each ABBV-154 dose and placebo using CMH test adjusting for stratification factors. The points and CI estimate of the treatment difference for each ABBV-154 dose versus placebo will be presented.

One supplementary analysis for the primary endpoint is to test a prespecified set of dose-response models among ABBV-154 dose groups and the placebo group at Week 12 of the Induction Period using the Multiple Comparison Procedure – Modeling (MCP-Mod) method.

Summary and Analysis of Secondary Endpoints

Analysis of secondary efficacy endpoints is described above.

Summary and Analysis of Additional Efficacy Endpoints

Analysis of additional efficacy endpoints is described above.

Subgroup Analysis for Efficacy

To evaluate the consistency of efficacy across demographic and other baseline characteristics, the following subgroup analysis will be performed on the primary endpoint: Baseline glucocorticoid use (yes; no)

- Endoscopic disease severity (SES-CD < 15; SES-CD ≥ 15)
- Inadequate response to adalimumab (yes; no)
- Sex (female; male)
- Race (White; Non-white)

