APPENDIX D. ACTIVITY SCHEDULE

The following table shows the required activities across the 12-Week Induction Period, the 12-Week Re-Induction Period, and the 40-Week Maintenance Period subject encounters. The individual activities are described in detail in the **Operations Manual** ([Appendix F](#)). Allowed modifications due to state of emergency or pandemic situations are detailed in the Operations Manual.

Study Activities Table

12-Week Double-Blind Induction Period

Activity	Screening	Visit Induction Period (Week)						Premature Discontinuation	Follow-up 70-Day Visit	
		Baseline (Week 0, Day 1)	2	4	6	8	10			12
INTERVIEWS AND QUESTIONNAIRES										
Subject information and informed consent	✓									
Confirm Eligibility	✓	✓								
Medical/Surgical History including disease specific history	✓	✓								
Alcohol use	✓									
Nicotine usage	✓									
Adverse Event Assessment	✓	✓	✓	✓	✓	✓	✓	✓	✓	✓
Record prior and concomitant medication/therapy	✓	✓	✓	✓	✓	✓	✓	✓	✓	✓
TB risk assessment questionnaire	✓									
SF-36		✓		✓		✓		✓	✓	
IBDQ		✓		✓		✓		✓	✓	
FACIT-Fatigue		✓		✓		✓		✓	✓	
PGIC-CD+				✓		✓		✓	✓	
PGIS-CD+		✓		✓		✓		✓	✓	
CDAI Components (may be performed at additional visits not marked if needed to confirm eligibility for Rescue Therapy)		✓	✓	✓		✓		✓	✓	
Automatic calculation of CDAI in EDC (may be performed at additional visits not marked if needed to confirm eligibility for Rescue Therapy)		✓				✓		✓		
Bowel Incontinence Scale		✓		✓		✓		✓	✓	
Dispense Subject Diary	✓									

Activity	Screening	Visit Induction Period (Week)							Premature Discontinuation	Follow-up 70-Day Visit	
		Baseline (Week 0, Day 1)	2	4	6	8	10	12			
Subject Diary Review		✓	✓	✓	✓	✓	✓	✓	✓		
Dispense wearable device (substudy only)		✓	Subject wears device continuously and measures stool frequency.								
Collect wearable device (substudy only)								✓			
 LOCAL LABS AND EXAMS											
Height	✓										
Body Weight	✓	✓	✓	✓		✓		✓	✓	✓	
Vital Signs	✓	✓	✓	✓		✓		✓	✓	✓	
Complete Physical Exam	✓	✓						✓	✓		
Symptom Directed Physical Exam			✓	✓		✓					
12-Lead ECG	✓							✓	✓		
Endoscopy (may be performed at additional visits not marked if needed to confirm eligibility for Rescue Therapy)	✓							✓	✓		
Automatic calculation of SES-CD score and endoscopic response status in EDC								✓			
Intestinal Biopsies	✓							✓			
DXA scan	✓										
Chest x-ray	✓										
Blood sample for anti-adalimumab antibody assay (where mandated by local requirements)	✓										

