3.0 Endpoints

In Section 3.0, please note

1. "Baseline" refers to the last available measurement on/before Baseline [Week 0, Day 1] of the Induction Period;
2. All endoscopic endpoints will be scored by central review;
3. Average daily liquid or very soft stool frequency (SF) and average daily abdominal pain (AP) score (SF/AP)-based efficacy endpoints will be analyzed in

the subset of subjects with an average daily liquid or very soft SF score ≥ 4 and/or average daily AP score ≥ 2 at Baseline.

The following endpoint definitions apply to the efficacy variables described below:

- **Endoscopic response:** decrease in Simple Endoscopic Score for Crohn's Disease (SES-CD) $> 50\%$ from Baseline (or for subjects with isolated ileal disease and a Baseline SES-CD of 4, at least a 2-point reduction from Baseline)
- **Clinical remission per CDAI:** CDAI < 150
- **Clinical response (CR100):** a decrease of CDAI ≥ 100 points from Baseline
- **Clinical remission per SF/AP:** average daily very soft or liquid SF ≤ 2.8 and not worse than Baseline AND average daily AP score ≤ 1 and not worse than Baseline
- **Enhanced Clinical Response per SF/AP:** $\geq 60\%$ decrease in average daily very soft or liquid SF and/or $\geq 35\%$ decrease in average daily AP score and both not worse than baseline, and/or clinical remission per SF/AP
- **Clinical response per SF/AP:** $\geq 30\%$ decrease in average daily liquid or very soft SF and/or $\geq 30\%$ decrease in average daily AP score and both not worse than Baseline
- **Endoscopic remission:** SES-CD ≤ 4 and at least a 2-point reduction versus Baseline and no subscore > 1 in any individual variable
- **Ulcer-free endoscopy:** SES-CD ulcerated surface subscore of 0 in subjects with SES-CD ulcerated surface subscore ≥ 1 at Baseline

Details of CDAI, SES-CD and patient-reported outcome (PRO) questionnaires are provided in [Appendix B](#), [Appendix C](#) and [Appendix D](#) respectively.

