9.0 Efficacy Analyses

9.1 General Considerations

All efficacy analyses will be conducted in the ITT Populations in each period. All tests will be 2-sided at an alpha level of 0.1.

For all efficacy endpoints, the descriptive statistics will be provided by treatment group for each of the study period. The statistics include number of observations, mean, standard deviation, 95% CI, minimum, median, and maximum for continuous variables, and number, percent and two-sided 95% CI for discrete variables. And number of subjects with missing data due to COVID-19 pandemic will be summarized for primary and secondary efficacy endpoints.

Unless otherwise specified, any subject will be analyzed according to the actual stratum the subject belongs to.

The Primary Analysis for the Induction Period and Re-Induction Period will be performed after all subjects have completed Week 12 of the Induction Period and Re-Induction Period, respectively, or prematurely discontinued study participation. This is the final efficacy analysis for the Induction Period and Re-Induction Period, respectively.

The final analysis will be conducted after all subjects have completed Week 40 of the Maintenance Period plus the 70 day Follow-up Visit or prematurely discontinued study participation. This is the final efficacy analysis for the Maintenance Period. To ensure the

integrity of the trial, the study sites and subjects will remain blinded until the final database lock is completed.

In Section 9.0, "Baseline" refers to the last non-missing observation prior to the first administration of study drug in the Induction Period, unless specified otherwise. "Comparison of treatment groups" refers to (i) comparison of each ABBV-154 group and placebo group in the Induction Period; (ii) comparison of Re-Induction Group 2 and Re-Induction Group 1 in the Re-Induction Period; (iii) comparison of each ABBV-154 group and placebo group for the randomized portion in the Maintenance Period.

"Stratification factors for the corresponding period" refers to randomization stratification factors specified in Section 2.3 except for the Maintenance Period, the randomization stratification factors used in efficacy analyses for the Maintenance Period are

- Achievement of CR100 at entry of the Maintenance Period (Week 12 of the Induction/Re-Induction Period): Yes vs No;
- Entry to the Maintenance Period: Induction Period vs Re-Induction Period.

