For the comparison between ABBV-154 80 mg SC EOW and Placebo in the Maintenance Period, all data from subjects of the corresponding ITT3/ITT3-RN population will be included.

For the comparison between ABBV-154 230 mg SC EOW and Placebo in the Maintenance Period, data from subjects of the corresponding ITT3/ITT3-RN population will be included with the exception that data from subjects who are randomized to Induction Group 1 (ABBV-154 150 mg IV + 80 mg SC EOW), considered as responder at Week 12 of the Induction Period and entered the Maintenance Period will not be included.

Analysis of Categorical Variables:

For categorical variables, frequencies and percentages will be reported for each treatment group in each of the study period. In each period, comparison of treatment groups will be performed using the Cochran Mantel-Haenszel (CMH) test adjusting for stratification

factors for the corresponding period. If there is a stratum that has no subject in it, a value of 0.1 will be added to the denominator to the corresponding stratum in order to prevent dividing by 0, as suggested in Greenland and Robins (1985).¹ Point estimates and 95% confidence intervals (CI) for the difference in proportions between treatment groups will be provided. Construction of CI for the common risk difference will be based on the Mantel-Haenszel estimate adjusting for stratification factors for the corresponding study period.

Analysis of Continuous Variables:

For continuous variables, the model based mean and standard error will be provided. The mean value of the variable at baseline and each scheduled visit will also be presented for each treatment group. Continuous variables collected longitudinally will be using a Mixed-Effect Model Repeated Measurement (MMRM) model. Continuous efficacy variables which are collected at only one post-baseline visit (such as SES-CD) will be analyzed using an Analysis of Covariance (ANCOVA) model. Point estimates and 95% CIs of mean change from baseline within each treatment group, and the difference between treatment groups for each period will be provided.

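### Maintenance models for continuous endpoints leave out the outcome's value at Maintenance entry; adding it (by visit in the MMRM) is an optional gain in precision

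*SAP*

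**What the plan says.** SAP 9.2.2 gives the MMRM fixed effects for treatment, visit and their interaction, plus "stratification factors at randomization, and the continuous fixed covariates of baseline measurement". The ANCOVA has the same terms without visit and is used for variables "collected at only one post-baseline visit (such as SES-CD"). SAP 9.5 applies both models to the randomised part of the Maintenance Period.

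Three statements settle what these models contain in Maintenance:

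- **Baseline.** In SAP Section 9 it "refers to the last non-missing observation prior to the first administration of study drug in the Induction Period" unless specified otherwise, and 9.2.2 specifies nothing else. Protocol 7.4 agrees: "baseline value (of the Induction Period) as a covariate".
- **Factors.** SAP 9.1 states that "the randomization stratification factors used in efficacy analyses for the Maintenance Period are" CR100 at entry (yes/no) and route of entry (Induction or Re-Induction).
- **Responses.** The MMRM is fitted "including observed measurements at all post-baseline visits for the respective analysis period", so the Week 12 value from the preceding period is not in the response vector.

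The entry values are already planned. Protocol Appendix D schedules CDAI components, IBDQ, FACIT-Fatigue, hs-CRP, FCP and endoscopy at Week 12 of both Induction and Re-Induction. It also lists "Automatic calculation of SES-CD score and endoscopic response status in EDC" at that visit. For analysis, SAP 3.0 says: "All endoscopic endpoints will be scored by central review".

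**The concern.** Subjects are re-randomised at Maintenance entry, so the value measured just before that point is a legitimate covariate. It is also closer in time to the Maintenance outcomes than the Induction Baseline, which precedes 12 or 24 weeks of treatment. CR100 at entry is a dichotomised change in CDAI. It recovers part of the entry information for CDAI and says little directly about IBDQ, FACIT-F, FCP, hs-CRP or SES-CD.

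At stake is the precision of the Maintenance treatment differences in CDAI, IBDQ, FACIT-F, FCP, hs-CRP, stool frequency, abdominal pain and SES-CD, with about 40 subjects per arm. These are other efficacy endpoints without type I error control, but they help describe two maintenance doses from which Protocol 4.2 expects Phase 3 doses to be chosen.

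**Working it through.** **The plan's own figure.** SAP 2.4 plans 40 per group, 11% against 37%, two-sided alpha 0.1, with power above 80%. With pooled rate 0.24:

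z = [0.26·√40 − 1.645·√(2·0.24·0.76)] / √(0.11·0.89 + 0.37·0.63) = (1.644 − 0.993)/0.575 = 1.131, so power is 87.1%.

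The figure reproduces. It concerns a binary endpoint analysed by CMH, so the covariate question does not touch it. The documents give no SD, correlation or power for any continuous endpoint; all correlations below are assumptions.

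**ANCOVA (SES-CD).** Let r be the partial correlation of the entry value with the Week 40 value, given the planned covariates. With 80 subjects and planned terms for treatment, CR100, entry route and Induction Baseline, adding the entry value multiplies the variance of the treatment difference by about (1 − r²)·74/73. The factor 74/73 is the cost of one more covariate. Equivalent size per arm is 40 divided by the ratio.

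| r | Variance ratio | Change | Equivalent n per arm |
|---|---|---|---|
| 0 | 1.014 | +1% | 39.5 |
| 0.2 | 0.973 | -3% | 41.1 |
| 0.3 | 0.922 | -8% | 43.4 |
| 0.4 | 0.852 | -15% | 47.0 |
| 0.5 | 0.760 | -24% | 52.6 |
| 0.6 | 0.649 | -35% | 61.7 |

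Simulation (20,000 trials, effect 0.55 SD) gave ratios of 1.013, 0.973, 0.851 and 0.650 at r = 0, 0.2, 0.4 and 0.6. Power moved from 76.9% to 76.4%, 77.2% to 78.0%, 76.8% to 82.2%, and 77.3% to 90.8%. With 10% of entry values missing and replaced by the mean pooled over arms, the ratios were 1.010, 0.966, 0.854 and 0.674.

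**MMRM (repeatedly measured endpoints).** Assume five visits, correlation a between the entry value and the first visit, and between-visit correlation ρ with AR(1)-type decay. The entry value's correlation with Week 40 is then r₅ = a·ρ⁴. With complete data and a large sample:

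- Entry value by visit: ratio = 1 − r₅².
- One common slope b: ratio = 1 − 2·b·r₅ + b², which exceeds 1 when b > 2·r₅.

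For (a, ρ) = (0.6, 0.7), r₅ = 0.6·0.7⁴ = 0.144. By visit, the ratio is 1 − 0.021 = 0.979. The maximum-likelihood common slope is 0.413, pulled up by the early visits, giving 1 − 0.119 + 0.171 = 1.052. The same steps give 1.092 (common) and 0.972 (by visit) at (0.7, 0.7), and 0.863 and 0.845 at (0.6, 0.9).

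Simulated change in Week 40 variance at 40 per arm (4,000 trials per setting, Monte Carlo SE of each ratio 0.02 or less), common slope / by visit:

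| Setting | Complete data | 30% random dropout by Week 40 |
|---|---|---|
| (0, 0.7) | 0% / +1% | +1% / +1% |
| (0.6, 0.7) | +6% / -1% | +7% / 0% |
| (0.7, 0.7) | +8% / -2% | +11% / 0% |
| (0.6, 0.8) | -3% / -6% | +2% / -3% |
| (0.6, 0.9) | -17% / -17% | -10% / -12% |
| constant 0.4 | -16% / -16% | -15% / -15% |
| constant 0.6 | -37% / -37% | -35% / -35% |

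**Missing data.** The CDAI part of the Maintenance rescue rule (Protocol 5.4) is measured from Maintenance Baseline, and SAP 8.1 drops data from rescue onward. Conditioning on entry CDAI therefore suits the missing-at-random assumption. In simulations of that rule, however, adding it moved the Week 40 estimate by less than 2 CDAI points, and not always toward the truth. The case does not rest on this.

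**The case against.** The strongest reply is that the plan made a consistent choice: Protocol and SAP both name the Induction Baseline, and the change endpoints are defined from it. All primary and secondary endpoints are binary and analysed by CMH, and no decision rule in the documents depends on the continuous ones. The figure of 47 per arm belongs to the ANCOVA, while most of the endpoints listed use the MMRM. There, under decay at ρ = 0.7, the by-visit gain is 0 to 2%, within simulation error. Under decay, an entry-to-Week-40 correlation near 0.4 needs the most favourable setting shown (0.6·0.9⁴ = 0.39). Maintenance entrants are selected as responders, which may narrow the spread of entry values, and CR100 already takes some of the CDAI gain.

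Most of this stands and limits the point. The gain is unproven for this trial, could be close to nil for fast-fading measures, and should not be quoted as 47 per arm across all endpoints. None of it removes the omission or makes the addition risky: at worst the by-visit form costs about 1% of variance. The common-slope result criticises nothing in the plan; it shows which form any addition should take.

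**Conclusion.** The point holds as an optional improvement. The Maintenance-entry value is absent from the planned models and nothing elsewhere in the documents adds it. The planned analyses are valid without it because treatment is re-randomised. The sample size, the primary analysis and the Week 40 CMH analyses are unaffected.

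At 40 per arm, the ANCOVA variance changes by +1% to -35% for partial correlations from 0 to 0.6. The by-visit MMRM changes by about +1% to -37% with complete data, and +1% to -35% with 30% dropout. The low end applies when correlation fades quickly over 40 weeks, the high end when it persists. These sizes rest on assumed correlations, five assumed visits and the planning figure of 40 per arm.

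**What to change.** 1. **Maintenance ANCOVA:** keep the Induction Baseline value and add the outcome's value at Maintenance entry (Week 12 of Induction or Re-Induction, whichever precedes entry). For SES-CD use the central read, to match the endpoint, although the re-randomisation decision uses the local read.
2. **Maintenance MMRM:** keep the Induction Baseline value and add the entry value with an entry-value-by-visit interaction, not a single common slope.
3. **Missing entry values:** state a rule, for example the last non-missing value before the first Maintenance dose, otherwise the mean pooled over arms.
4. **Consistency and timing:** align the covariate sentence in Protocol 7.4, or record the departure in the SAP. Fix the wording before any Maintenance unblinding, including the possible Maintenance interim in SAP 11.0.

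Leave the main Week 40 CMH analyses as planned. Stratifying Week 40 endoscopic response by entry endoscopic status is at most an optional sensitivity analysis; its effect on power was about -1 to +4 points, with the sign not known in advance.

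The cost is an edit to SAP 9.2.2 and one Protocol sentence, with no new data. It adds five MMRM parameters with five visits, and about 1% more variance if the entry value proves uninformative.

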9.2.3 Additional Analyses

In addition, As Observed (AO) analysis will be performed as supplementary for categorical endpoints.

- AO: The AO analysis will not impute values for missing evaluations, and thus a subject who does not have an evaluation on a scheduled visit will be excluded from the AO analysis for that visit. AO will include all values collected in the study (except data collected after initiation of ABBV-154 rescue therapy for the analyses in the Maintenance Period).

9.3 Primary Efficacy Endpoint and Analyses

9.3.1 Primary Efficacy Endpoint

The primary endpoint for the primary analysis of efficacy is:

- Achievement of endoscopic response at Week 12 of the Induction Period

9.3.2 Primary Analysis of Primary Efficacy Endpoint

The attributes of the estimand corresponding to the primary efficacy endpoint are summarized in [Table 1](#).

The primary endpoint will be analyzed between each ABBV-154 group and placebo group in the Induction Period using the CMH test, stratified by the randomization factors (baseline glucocorticoid use (yes/no); endoscopic disease severity (SES-CD < 15; SES CD \geq 15); inadequate response to adalimumab (yes/no)) based on ITT1 population.

Table 1. Summary of the Estimand Attributes of the Primary Efficacy Endpoint

Estimand Label	Attributes of the Estimand				Statistical Summary
	Treatment	Endpoint	Population	Intercurrent Events	
Primary	Each ABBV-154 group vs. placebo in the Induction Period	Achievement of endoscopic response at Week 12 of the Induction Period	Subjects with moderately to severely active CD who had inadequate response to or were intolerant of prior biologics	IE1: Initiation or dose escalation of CD-related confounding medications IE2: premature discontinuation of study drug All subjects will be considered as non-responders at or after IE1 All data after IE2 will be used until initiation of CD-related medications	Difference in the proportion of subjects achieving endoscopic response

The primary efficacy endpoint will be tested at two-sided significance level of 0.1. A CMH based two-sided 95% CI for the difference between treatment groups will be constructed.

The NRI-C approach for handling missing data will be used for main analysis for the primary endpoint.

